1. Participants randomised to ApBM will consume significantly fewer standard drinks per week than participants in the minimal condition, as measured using self-report 4 weeks after commencing training (post-intervention; primary endpoint), and at 1-month and 3-month follow-ups (secondary endpoints).

Secondary outcomes:

2. Participants randomised to ApBM will show significantly larger declines, compared to those in the minimal condition, in past-week frequency of alcohol craving at post-intervention and follow-up assessments (relative to baseline craving frequency), as assessed by the frequency scale of the Craving Experience Questionnaire.
3. Participants randomised to ApBM will show significantly larger declines than those in the minimal condition in Severity of Dependence Scale scores at post-intervention and follow-up assessments (relative to baseline craving frequency).
4. Participants randomised to ApBM will show significantly larger declines than those in the minimal condition in Alcohol Use Disorders Identification Test (AUDIT) scores at the 3-month follow-up (relative to baseline scores).
5. Participants randomised to ApBM will have significantly fewer past-week heavy drinking days (HDDs, defined as ≥ 5 standard drinks in a day) than participants in the minimal

condition, as measured using self-report at post-intervention, 1-month, and 3-month follow-ups. Past-month HDDs will also be analysed post-intervention.

6. Participants randomised to ApBM will have significantly fewer past-month drinking days (i.e., days on which any alcohol is consumed) post-intervention and at 1- and 3-month follow-ups.
7. The proportion of participants reporting complete abstinence (i.e., 0 days on which any alcohol was consumed – both past week and past month will be analysed) will be significantly higher among participants in the ApBM than among those in the minimal condition at post-intervention and follow-up assessments.
8. Participants receiving ApBM will experience larger increases than those in the minimal condition in quality of life and health (assessed with 3 Australian Treatment Outcome Profile items) at post-intervention and follow-up assessments (relative to baseline).
9. There will be a significantly greater reduction in approach bias, as measured by the alcohol approach avoidance task, in participants assigned to the ApBM condition, compared to those in the minimal condition, between baseline and post-intervention.

Methods

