Design & Setting: We will conduct a double-blind, randomised, parallel-group controlled superiority trial with alcohol treatment outpatients at 6 AOD treatment services in Melbourne, Victoria. Participants will be randomised to one of 2 groups with a 1:1 allocation ratio. Both participants and researchers completing the follow-up interviews will be unaware (blinded) of the condition to which they have been randomly allocated.

Participants: We aim to recruit at least 300 participants receiving outpatient interventions for alcohol use disorder at the participating services. To be eligible, participants must, at the time of the screening interview:

- Be aged 18+
- Own an Android or iOS smartphone with an Australian mobile number
- Be currently accessing outpatient treatment for alcohol problems. (There is no requirement that alcohol be the *only* substance for which they are seeking treatment, and as such participants with multiple drugs of concern are eligible as long as alcohol is one of the drugs of concern for the current episode of treatment.)
- Have an Alcohol Use Disorders Identification Test (AUDIT) score of at least 8
- Not have been in residential rehabilitation within the past 4 weeks.
- Not have been in any form of inpatient treatment (e.g. hospital or residential withdrawal treatment) within the past week.
- Not entering inpatient/residential treatment within the next month.

The target sample size was determined based on practical considerations (likely recruitment rate, time available for recruitment), as there was little prior basis to estimate likely effect size of a personalised ApBM smartphone app in an outpatient client population. Nevertheless, a calculation conducted in GPower 3.1 suggested that the primary analysis (across 4 repeated measures) would have 90% power to detect a small time x group interaction effect size (partial eta squared of .01) with a sample of 178 participants (i.e., 59% retention at follow-ups). If recruitment proceeds quickly enough, we will aim to recruit more than 300 participants, to allow for increased statistical power in case attrition is larger than expected.

Measures:

Demographic information: Participants will be asked to enter their gender, the AOD service where they were recruited from, the date they began the current episode of treatment they are receiving from that service, and drugs of concern, in an online survey hosted on Qualtrics.

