Audio-recorded qualitative interviews and verbal consent will be stored as .mp4 files on a secure Google drive hosted by Monash University, access to which will be restricted to project personnel (but which will not be made accessible to blinded quantitative data collectors until data collection is complete). The .mp4 files will be securely transferred to Pacific Transcription, a trusted transcription service provider that is frequently used by Monash University and Turning Point. To preserve participant anonymity the recording of verbal consent (where the participant states their full name and is also asked about their phone number) will be separated from the rest of the file and stored separately, while the main interview file will be labelled with a participant number (this number will be the same as the participant access code used to access the app, allowing baseline demographic data to be matched to qualitative interview data), not their name. Transcripts returned by Pacific Transcription will be stored as .docx files on the secure Google drive until data collection is complete. Once data collection is complete and blinding no longer required, these files will be stored in the project folder on the Turning Point Clinical Research Drive. They will be deleted from the Google Drive once analysis and publication is complete, and stored for at least 7 years following publication of the last paper arising from this study, or 7 years after the final report to the ethics committee, or 7 years after final reporting of outcomes on the clinical trials registry, whichever occurs latest.

Data Analysis

Statistical significance will be ascertained using $\alpha=.05$. Any participants who commenced at least 1 session of ApBM (if in the ApBM condition) or AAT (if in the minimal control condition) will be included in the analysis population.

Primary outcome: A linear mixed-effects model (LMM) will be used to compare change in mean standard drinks consumed per week between groups across 4 time points (baseline, post-intervention, 1-month follow-up, and 3-month follow-up). This model will test the main effects of time and group and (most crucially for determining efficacy) the group x time interaction. Planned follow-up comparisons between groups at post-intervention, 1-month follow-up, and 3-month

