follow-up time-points will be conducted using t-tests, with post-intervention being the primary endpoint. A secondary sensitivity analysis will be conducted excluding a participant's data from any time-point where they had been in residential/inpatient treatment in the past week (i.e., restricting analyses to time-points where a participant's opportunity to drink had not been limited by hospitalisation, rehabilitation, etc.). If a difference between groups is found post-intervention, a secondary LMM analysis of difference between groups in change in weekly standard drinks during the intervention period (i.e., 5 levels of time: Baseline, week 1, week 2, week 3, post-intervention) will be conducted to examine how quickly differences between groups emerge, with t-tests used to compare groups at week 1, 2, 3, and post-intervention time-points. This secondary analysis will be conducted excluding participants who had engaged in any residential/inpatient treatment within the intervention period.

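### The 90% power quoted for a partial eta squared of .01 belongs to a larger effect (about .027 in the ordinary sense), and the inputs that produce it are not stated

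*Combined protocol and SAP*

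**What the plan says.** The sample-size text under Methods, Participants, sets a target of at least 300 and explains that "The target sample size was determined based on practical considerations". It then offers a GPower 3.1 calculation in support, made for the main model with its four measurement occasions, and reports "90% power to detect a small time x group interaction effect size (partial eta squared of .01) with a sample of 178 participants". It equates 178 with "i.e., 59% retention at follow-ups"; 178/300 is 59.3%.

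Data Analysis sets alpha at .05 and specifies a linear mixed model over baseline, post-intervention, 1 month and 3 months. The term it singles out is ("most crucially for determining efficacy) the group x time interaction"). The same section plans t-tests between groups at each visit after baseline, "follow-up time-points will be conducted using t-tests, with post-intervention being the primary endpoint". Hypothesis 1 names the same primary endpoint.

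Neither the sample-size text nor any other section gives the assumed correlation among repeated measures, the nonsphericity correction epsilon, or the definition of effect size used in the program.

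**The concern.** Partial eta squared ordinarily means SS effect/(SS effect + SS error), where the error is the within-participant residual. On that definition power follows from the effect, N and the degrees of freedom, with no correlation to choose, and .01 at 178 participants falls far short of 90%. A different convention scales the effect to the SD of the raw scores within each group-by-time cell and brings the correlation in separately. The same label, .01, then stands for a larger effect on the ordinary scale.

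The sentence is there to reassure: even with 59% retention, the trial would keep 90% power for a small effect. If the label and the power come from different scales, a reader cannot tell what size of effect that reassurance covers. This matters most if the trial finds no difference, because the power statement then decides what the result rules out.

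**Working it through.** **Inputs from the documents.** Two groups, 1:1; m = 4 repeated measures; N = 178; alpha .05; partial eta squared .01, so f² = .01/.99 = .010101 and f = .1005. Degrees of freedom: df1 = (2 − 1)(4 − 1) = 3; df2 = (178 − 2) × 3 = 528.

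**Inputs assumed.** Correlation ρ and epsilon ε, neither of which is stated.

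**Step 1. Reproduce the plan's figure.** Scale f to the within-cell SD: λ = f² N m ε/(1 − ρ), with both degrees of freedom multiplied by ε. With ρ = .5 and ε = 1:

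λ = .010101 × 178 × 4/.5 = 14.38.

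The noncentral F then gives power .902. At N = 176, λ = 14.22 and power is .899. So 178 is the smallest even N that reaches 90%, as the plan states.

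**Step 2. Convert that effect to the ordinary scale.** Partial eta squared = λ/(λ + df2) = 14.38/(14.38 + 528) = .0265, about .027.

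As a mean difference: let the group difference be 0 at baseline and D SD at each later visit. The interaction variance is the mean squared deviation of (0, D, D, D) about its mean, .1875 D², divided by 4 for two equal groups. Hence f = D × √.046875 = .2165 D, and D = .1005/.2165 = 0.46 SD.

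**Step 3. Power for .01 in the ordinary sense.** Here λ = f² × df2, and no correlation enters.

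| Complete cases | df2 | λ | Power |
|---|---|---|---|
| 178 | 528 | 5.33 | 46% |
| 300 | 894 | 9.03 | 71% |
| 470 | 1404 | 14.18 | 89.9% |
| 472 | 1410 | 14.24 | 90.1% |

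At ρ = .5 this smaller effect is a constant difference of 0.46 × √(5.33/14.38) = 0.28 SD.

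**Step 4. Allow for partial data.** The mixed model would also use data from the 122 who do not complete. Information was computed for 300 randomised and 178 complete under compound symmetry, with the effect fixed at the ordinary .01 and ρ from .3 to .7. Several effect profiles were tried (constant, linear, post-intervention only, last visit only), with dropouts leaving after baseline, after post-intervention, after 1 month, or spread over these visits. Power runs from about 47% to 69%. The profile, dropout pattern and ρ are all assumptions; the documents give none of them.

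**Step 5. Sensitivity of the plan's own figure to ρ** (Step 1 convention, 178 complete, ε = 1).

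| ρ | Power at 178 | Smallest even N for 90% |
|---|---|---|
| .3 | 77% | 248 |
| .4 | 84% | 212 |
| .5 | 90% | 178 |
| .6 | 96% | 142 |
| .7 | 99% | 108 |

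With ρ = .5 and ε = .8, power is 85%.

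**Step 6. The post-intervention t-test.** Two-sided alpha .05 and 90% power (noncentral t) correspond to a difference of 0.49 SD with 89 per arm and 0.38 SD with 150 per arm.

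**The case against.** The strongest reply is that nothing has been miscalculated. The figure reproduces exactly with round inputs in a convention that is legitimate. Other pairs can be tuned to 178 (ρ .55 with ε .86, or ρ .60 with ε .73), but the round values near them miss it: .55 with .85 gives 180, .55 with .90 gives 172, .60 with .75 gives 174 and .60 with .70 gives 184. So ρ .5 with ε 1 is the evident choice. All of that stands, and it rules out calling this an arithmetic error.

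A reader might also infer that the trial really has 46% power where 90% was claimed. The documents do not support that. The 46% belongs to a smaller effect than the one evidently entered. For the effect evidently entered, at ρ .5 and ε 1, counting dropouts' partial data raises power to about 95% if they all leave after baseline and about 98% if dropout is spread over the visits, for a constant difference.

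It can also be said that N does not rest on the calculation, and that the calculation addresses the interaction the analysis section treats as decisive. Both are true. They lower the stakes and make a separate figure for the t-test optional. They do not make .01, in its usual meaning, the effect that has 90% power.

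**Conclusion.** The power statement is wrong as written because it pairs 90% with an effect size that, in its ordinary sense, does not have that power. Under the likely inputs the effect detectable with 90% power is a partial eta squared of about .027, not .01. An ordinary .01 has about 46% power with 178 complete cases, 71% with 300, and roughly 47–69% when partial data are counted under the assumptions in Step 4. All of these are well below 90%.

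The .027 rests on ρ = .5 and ε = 1, which are inferred. The 0.46 SD further assumes a constant difference after baseline. The complete-case figures for an ordinary .01 need no correlation but do take ε = 1. Because the plan's 90% moves with the unstated ρ, it may be optimistic or conservative.

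Severity is modest: the target N, the design and the analysis are unaffected.

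**What to change.** Reword the sentence and leave N as it is.

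- State the effect-size convention, the correlation and the epsilon entered in GPower.
- Then either restate the effect detectable with 90% power as a sum-of-squares partial eta squared (about .027 if ρ .5 and ε 1 were used), or keep .01 in its ordinary sense and give its power: about 46% with 178 complete cases and 71% with 300.
- Show power over a range of correlations, such as .3 to .7.
- Optionally, add the detectable difference for the post-intervention t-test, with the retention it assumes: 0.49 SD with 89 per arm, 0.38 SD with 150 per arm.

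The cost is a change of protocol wording. The drawback is that either the stated detectable effect or the stated power becomes less favourable.

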Alcohol craving: The Craving Experience Questionnaire frequency scale (CEQ-F) (May et al., 2014) will be used to measure the frequency of alcohol cravings over the past week. This is a 10-item scale, with each item rated on a scale of 0-10. Total scores are calculated based on the mean of individual items. Items can also be broken down into 3 subscales: "intensity" (3 items), "imagery" (4 items), and "intrusiveness" (3 items). The CEQ-F has an internal consistency of .94 and intercorrelations within each sub-scale range from .63-.73 (May et al., 2014).

In addition to the CEQ, we will also utilise a single-item visual analogue scale (VAS) to measure current intensity of alcohol craving immediately before and after each ApBM and AAT session. Participants will be asked "How strongly are you craving alcohol right now?", with a line displayed below the question and a slider that they can place between ends anchored with the words "not at all" on the left end and "extremely" on the right. A participants' placement of the slider will be converted to a number ranging from 0-100 for data storage. If participants provide a score of 90 or higher on the post-test VAS (i.e., immediately after completing an ApBM or AAT session), the app will prompt users with an additional support dialogue which links users to the National Alcohol and Other Drug Hotline and Counselling Online (www.counsellingonline.org.au).

Alcohol consumption: At baseline, participants will be asked to estimate the number of days on which they consumed alcohol out of the past 28 days and the number of standard drinks consumed on each day of the past week. To do this, they will be shown a calendar chart displaying the past 4 weeks, which will first be displayed with the most recent week in this period (i.e., 1-7 days ago) highlighted. For each day in this week, they will be asked to select a number ranging from 0-80 to indicate their estimate of how many standard drinks they consumed on that day in that week. Past-

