Minimal (control) group: Control participants will receive a minimal version of AAT-App which does not include any ApBM training or picture selection component, and only includes the weekly alcohol consumption questions, a weekly AAT task, and the VAS craving measure. Upon opening the app for the first time, participants are informed that they will be using "an app designed to target their alcohol use and awareness". Instead, participants are told that the "brain-training" will involve completing one training task at the end of each week, and answering some questions about their weekly alcohol consumption.

After reading the opening page's instructions, participants will then complete the alcohol consumption questions, before completing the pre-training VAS, the AAT, and the post-training VAS. The VAS is included so that cravings can be monitored before and after completing the AAT, where participants can access additional support if they indicate that their cravings are extreme (i.e., through links to Counselling Online and the National Alcohol and Other Drug Hotline). At the end of week 1 (i.e., 7 days post-baseline) participants will receive a notification reminder to complete the weekly alcohol consumption questions, followed by the pre-training VAS, AAT and post-training VAS. This process is repeated at the end of each week throughout the intervention period (i.e., 14-, 21- and 28-days post-baseline).

Procedure: Staff at participating services will briefly describe the study to clients who they believe may meet eligibility criteria. To allow for blinding, no specific details will be provided regarding approach bias modification, and participants will merely be informed that the study tests "a new smartphone 'brain-training app'" that "involves doing brief game-like tasks on your phone each week for 4 weeks". Clients who are interested will be asked to sign a form providing consent for the treatment service to provide their phone number to research staff. In the event they are unable to sign the form (e.g., if not present in person due to a telehealth appointment), clients can give verbal consent for the clinician to sign the form on their behalf. Clinicians can also complete the form online via Qualtrics Plus, by scanning a QR code on the paper form which directs them to an online

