Data will be exported from Qualtrics in excel and/or csv file formats for storage and analysis on Turning Point's Clinical Research shared drive. Access to the project folder will be restricted to project team members, such that the folder can only be opened on a computer where a designated team member is logged in using their password-protected Eastern Health login. In-app alcohol use data and back-end user metrics (number of sessions commenced; number completed; session duration and total score; AAT trial reaction time, trial type, and error data; weekly and monthly alcohol consumption data; pre- and post-AAT VAS craving data; and pre- and post-ApBM VAS craving data) will be stored on a secure Google Firebase server, with the database only accessible to project personnel and the app developers (ANT Development Studios). These data will be exported in csv format for storage in the restricted-access project folder located on Turning Point's Clinical Research shared drive at the end of the study.

Data will be merged into single files, as necessary, for statistical analyses. Google Firebase datasheets will list participants' access codes, not their phone numbers, while Qualtrics datasheets will include phone numbers but not access codes. Thus, a separate spreadsheet will be stored on a password-protected Google drive hosted by Monash University, and shared only with research team members, in which the correspondence between phone numbers and access codes will be recorded. This sheet will allow Google Firebase and Qualtrics data to be linked at the individual level. Merged datasheets may be uploaded to team member's personal, password-protected Monash University

online drives where analyses require access to statistical software available through Monash University that is not available on Turning Point computers. However, statistical analysis files will need to be exported for storage on the Turning Point Clinical Research drive and deleted from team member's Monash drives once statistical analyses are complete, such that long-term storage of data following completion of the project will only be on the Turning Point drive. As such, data stored on Qualtrics, Google Firebase, and Google drives will also be deleted from these locations after publication of findings are complete and all data has been exported and stored on the Turning Point drive.

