- 5 Defining and naming themes: Developing a detailed analysis of each theme, determining the 'story' of each.
- 6 Writing the manuscript: Weaving analytic narrative and data extracts, contextualising the analysis in relation to existing literature, remaining open to revising themes even at this stage.

The coding process will be primarily conducted by two researchers, and a third researcher will oversee and verify coding decisions in order to ensure agreement and consistency throughout the process. To avoid possible conflicts of interest, neither [name] nor [name] will be involved in qualitative data collection, coding or analysis. The digital qualitative data analysis software NVivo 11.4.0 will be used to facilitate qualitative data analysis.

Free-text responses to app acceptability questions in the post-intervention survey will be reviewed primarily to identify reports of functionality issues (e.g., "bugs" in the app) and safety issues (e.g., reports of triggering). Any such issues will be catalogued to inform further improvements to the app (if necessary) and its delivery/implementation in future research and/or treatment contexts. As we do not expect these data to be as thematically rich as data derived from interviews, and they are therefore less likely to contribute to publications, we do not anticipate applying an analysis protocol as formal as that applied to interview transcripts.

Interim analyses: There are no planned interim analyses of either quantitative or qualitative data. The pre-planned analyses are intended to be conducted after all data has been collected. Nevertheless, interim analyses will be permitted if necessary for student projects (e.g., an honours project where data analysis and thesis writing is required to be completed prior to the project end date). In this case, the unblinded research officer or statistician will provide the student with the randomisation sequence and the student will be instructed not to share this with anyone else.

Dissemination

We intend to submit at least one manuscript describing quantitative outcomes and at least one describing qualitative findings to peer-reviewed academic journals. All principal investigators, as well as [name] and [name], will be eligible for authorship of the manuscript describing the primary outcome, along with anyone else deemed by the coordinating principal investigator to have

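### The plan's dedicated information on craving harm comes only from people who reach the day-28 survey, while the craving ratings stored at each app session have no safety summary

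*Combined protocol and SAP*

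**What the plan says.** **Collection.** Under Measures, Alcohol craving, a single-item visual analogue scale (VAS) is used "to measure current intensity of alcohol craving immediately before and after each ApBM and AAT session". Data management lists among the stored app data "pre- and post-AAT VAS craving data; and pre- and post-ApBM VAS craving data", alongside the numbers of sessions begun and finished. The Intervention section places the post-session rating at the end of the task.

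**Support dialogue.** Alcohol craving gives a specific rule: "If participants provide a score of 90 or higher on the post-test VAS", the app links the user to support services. The Minimal (control) group section describes it more loosely: "The VAS is included so that cravings can be monitored before and after completing the AAT". It adds that help is on offer to people who report extreme craving, without giving a cut-off.

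**Analysis.** The VAS is not among the continuous outcomes listed under Secondary outcomes. It appears once, under Psychometric properties of AAT, where pre-session scores are among the variables correlated with baseline alcohol approach bias.

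**Dedicated harm information.** App acceptability includes a 5-point item on whether the app increased cravings, which Secondary outcomes describes within each group. The other source is the free-text comments: "Free-text responses to app acceptability questions in the post-intervention survey will be reviewed primarily to identify reports of functionality issues", and also safety issues, with triggering given as the example. According to Procedure, both belong to a survey whose in-app link appears after the day-28 drinking questions and AAT and expires after 1 week.

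**Analysis population.** The Data Analysis section includes anyone who began at least one ApBM session (active arm) or one AAT session (control arm).

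**The concern.** Craving provoked by alcohol cues is the obvious acute risk of this intervention. The two sources meant to detect it depend on a participant staying with the app for four weeks, doing a further task with alcohol pictures and then answering a survey in time. Someone who began sessions and then stopped can be counted in the analysis population yet has no entry in either source. The app will already hold that person's ratings from the sessions they did, and a record of sessions begun but not finished. Without a planned summary, the trial could report favourable survey ratings from those who stayed, with nothing pre-specified to show how craving behaved within sessions among those who did not.

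**Working it through.** The plan gives no figure on this point to reproduce. The check compares sections and adds a few counts.

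**Step 1. What is stored and what is used.**

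| Data held by the app | Planned use |
|---|---|
| Pre-session VAS, both tasks | Exploratory correlation with baseline approach bias |
| Post-session VAS, both tasks | Opens the support dialogue in the app; no analysis |
| Sessions begun and sessions finished | None stated in the Data Analysis section |

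**Step 2. Scheduled ratings per participant.** Procedure asks the active arm for at least 2 ApBM sessions a week for 4 weeks, so at least 2 x 4 = 8, plus the AAT at baseline and day 28: 8 + 2 = 10 sessions or more. The control arm does the AAT at baseline and days 7, 14, 21 and 28: 5 sessions. With one rating before and one after each session:

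- active: at least 10 + 10 = 20 ratings, of which at least 10 are post-session;
- control: 5 + 5 = 10 ratings, of which 5 are post-session.

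**Step 3. Exposure to alcohol pictures.** An ApBM session shows 6 x 13 = 78; an AAT session shows 20 x 2 = 40. As scheduled, the active arm sees at least 8 x 78 + 2 x 40 = 704 and the control arm 5 x 40 = 200, a ratio of about 3.5. This measures exposure, not harm.

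**Step 4. Why the denominator must be sessions.** Suppose, as an assumption not in the documents, that every session in either arm has the same independent chance q of a post-session rating of 90 or more. The chance that a participant has at least one such rating in n sessions is 1 - (1 - q)^n.

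| q | n = 5 (control, as scheduled) | n = 7 (active, 5 ApBM + 2 AAT) | n = 10 (active, minimum schedule) |
|---|---|---|---|
| 1% | 4.9% | 6.8% | 9.6% |
| 5% | 22.6% | 30.2% | 40.1% |
| 10% | 41.0% | 52.2% | 65.1% |

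The middle column uses the feasibility study's median of 5 ApBM sessions. With identical risk per session, a per-person count would still make the active arm look worse. Active participants may also do unlimited extra sessions.

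**Step 5. What the sessions common to both arms can show.** Both arms do the AAT at baseline and day 28. Procedure places the baseline AAT before the first ApBM session, so it carries no information on ApBM harm. The day-28 AAT exists only for people still using the app, and shows fixed images rather than those chosen for training. Neither gives a clean comparison of ApBM harm between arms.

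**Step 6. The two descriptions of the support dialogue.** Alcohol craving names a cut-off and a rating (post-session) and covers both tasks. The Minimal (control) group section names neither, mentions monitoring before and after, and covers only the AAT. It can be read as a loose summary of the specific rule, but the wording differs.

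**The case against.** The plan is not silent on worsening. The Craving Experience Questionnaire frequency scale (CEQ-F) is compared between arms at post-intervention, 1 month and 3 months, and drinking is reported in the app on days 7, 14, 21 and 28. Survey non-responders get an SMS and then contact from a blinded researcher. Interviews with 20 active-arm participants ask about effects on craving and drinking. All of this stands, so a reader should not infer that people who stop are missing from every measure that could show harm. What remains is narrower: CEQ-F covers past-week frequency, drinking reports do not measure craving, and the interviews draw on one arm and on people who completed the 1-month survey. None records the acute response within a session.

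A reader might also infer that sessions will be abandoned because of craving. The documents do not support that: no reason for stopping is listed among the stored data, and what the app does when a session is left or resumed is not described. Nor do the two descriptions of the dialogue set rival triggers, since the looser one does not say that a pre-session rating opens it.

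Finally, post-session ratings do not exist for unfinished sessions, so no VAS table fully covers the people of most interest. That is correct. It is why the proportion of sessions not completed is needed beside the VAS change.

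**Conclusion.** The concern holds as a gap in the planned safety analysis. The dedicated craving-harm sources are restricted to people who reach the day-28 survey, and the stored session data that extend to people who stopped earlier have no safety summary. As scheduled, at least 10 post-session ratings per active participant and 5 per control participant go unanalysed. This is a cheap improvement to the analysis plan. It does not threaten the primary result.

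The share of participants affected cannot be derived from the documents. Two available figures may tempt a reader and should not be used. The 59% retention (178/300), hence about 41% loss, comes from the power calculation for follow-ups and does not forecast day-28 survey response. The 31% completing at least 8 sessions comes from an open-label community study in which only 9% were in formal treatment, and says nothing about sessions left midway.

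The documents contain no evidence that harm occurs. The conclusion assumes that sessions are logged as Data management describes. That list does not say whether the begun and finished counts are kept separately for ApBM and AAT; the stored AAT trial data should help to identify unfinished AAT sessions.

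**What to change.** Add to Data Analysis, Secondary outcomes, a descriptive safety table by arm and by task (ApBM, AAT), covering everyone who began a session of either task, including those who later stopped. Report:

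- post-minus-pre VAS change per completed session;
- the proportion of completed sessions with a post-session VAS of 90 or more (the plan's own cut-off, used here only to describe);
- the proportion of begun sessions not completed, with the pre-session VAS for those sessions where recorded.

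Use sessions as the denominator and give the number of participants contributing to each cell. State that reasons for stopping are not recorded. Do not present the baseline AAT as evidence on ApBM harm, and label any day-28 AAT comparison as limited to people still engaged.

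Separately, reconcile the Alcohol craving and Minimal (control) group sections so that they describe the support dialogue in the same terms. Which rating should open it is a clinical decision outside this review.

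The cost is a wording change and one table from data already held, with a little more analysis work. No new data collection is needed.
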